11.1.6.2 Secondary Variables

DoR, CBR, and PFS will be based on the response assessments by the Investigator. Secondary analyses will be conducted using either the CAE population or the FAS as described within each variable section below.

11.1.6.2.1 Clinical Benefit Rate (CBR)

Descriptive statistics for CBR, confirmed CR, PR or SD based on the response assessments by the Investigator will be presented by strata and treatment arm using both the FAS and the CAE population. Exact 95% Clopper-Pearson CIs for CBR will also be presented.

11.1.6.2.2 Duration of Response (DoR)

DoR will be summarized descriptively using a subset of the CAE population (patients who have confirmed CR or PR), presenting Kaplan-Meier (KM) estimates for the median, 25th and 75th percentiles and their two sided 95% CIs (Brookmeyer and Crowley, 1982) where appropriate. In addition, minimum and maximum values will also be displayed.

DoR will be listed and KM plots will also be provided.

Censoring Rules for DoR

- Patients without documented PD will be censored at the date of the last evaluable tumor assessment prior to the start of the new therapy (if received any), unless they die within 122 days of last evaluable tumor assessment, in which case they will be assessed as having an event on the date of death.

11.1.6.2.3 Progression-Free Survival (PFS)

PFS will be summarized in the same manner as DoR, though conducted using the FAS. In addition, the PFS rate at 3, 6 and 9 months will be analyzed using KM methodology (Greenwood's formula, Kalbfleisch and Prentice, 1980).

Censoring Rules for PFS

- Event time will be censored on the date of first dose with duration of 1 day for;
 - No Disease Assessments Performed On-Study
i.e. Patients lacking evaluation of disease after first study treatment, unless they die within 2 tumor assessments of baseline (on or prior to week 16, i.e. Cycle 5 Day 1 plus the 10 day window, which is Study Day 122), then they will be treated as experiencing an event with date of death as the event date.
 - Patients with baseline or post-baseline assessments inadequate to apply RECIST v1.1 criteria.
- Patients without documented PD will be censored at the date of the last evaluable tumor assessment prior to the start of the new therapy (if received any), unless they die within 122 days of last evaluable tumor assessment, in which case they will be assessed as having an event on the date of death.

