9.4.3 Duration of Response

Duration of Response (DR) is defined as the time from date of the first documentation of objective tumor response (CR or PR) to the first documentation of Objective Progression of Disease (PD) or to death due to any cause in the absence of documented PD. Censoring for the DR endpoint will be assigned on the date of the last tumor assessment if no assessment of tumor progression is identified and the patient does not die while on study. DR will only be calculated for the subgroup of patients with an objective response. The Kaplan-Meier method will be used to obtain the estimate of median DR.

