9.4.4 Progression Free Survival

Progression-free survival (PFS) is defined as the time from date of first study treatment to first PD or death due to any cause in the absence of documented PD. Censoring for the PFS endpoint will be assigned on the date of the last tumor assessment if no assessment of tumor progression is identified and the patient does not die while on study. For patients in whom two or more sequential assessments are missed, followed by the finding of tumor progression, the PFS endpoint will be censored on the date of the last tumor assessment before the gap. Patients lacking an evaluation of disease after first study treatment will have their PFS time censored on the date of first dose with duration of 1 day. Patients who start a new anti-cancer therapy prior to documented PD will have the endpoint censored at the date of the last tumor assessment prior to the start of the new

therapy. The Kaplan-Meier method will be used to obtain the estimate of median progression-free survival time.

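### SAP censoring rules for PFS and DoR depart from the protocol without being listed in SAP 4.1, and the fixed 122-day death limit does not follow the 16-week scan schedule

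*SAP*

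**What the plan says.** **Protocol 9.4.4 (PFS)** runs PFS from first treatment to progression (PD), or to death from any cause without PD. It then gives four censoring rules:

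- No PD: censor at the last assessment "if no assessment of tumor progression is identified and the patient does not die while on study" (9.4.3 has the same wording for DoR).
- Gap: "For patients in whom two or more sequential assessments are missed, followed by the finding of tumor progression, the PFS endpoint will be censored" at the last assessment before the gap.
- Never scanned after dosing: "Patients lacking an evaluation of disease after first study treatment will have their PFS time censored on the date of first dose", with no stated exception for death.
- New therapy: "Patients who start a new anti-cancer therapy prior to documented PD will have the endpoint censored" at the last assessment before that therapy.

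**SAP 11.1.6.2.3 (PFS)** gives two rules:

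- Day-1 censoring for patients with no on-study assessment, "unless they die within 2 tumor assessments of baseline" (set at Study Day 122), in which case the death is an event. Day-1 censoring also applies to "Patients with baseline or post-baseline assessments inadequate to apply RECIST v1.1 criteria".
- Patients without documented PD are censored at the last evaluable assessment before any new therapy, "unless they die within 122 days of last evaluable tumor assessment", in which case the death is an event.

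It contains no rule for PD found after missed assessments. It also states that "the PFS rate at 3, 6 and 9 months will be analyzed using KM methodology".

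**SAP 11.1.6.2.2 (DoR)** repeats the second rule. Protocol 9.4.3 has neither a time limit on deaths nor a new-therapy rule.

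SAP 8.2.2 and 8.2.4 define death from any cause without PD as an event, with no time limit. SAP 4.1 lists changes for glesatinib, mocetinostat, the analysis populations, clinical benefit rate and the PK sub-studies, and nothing on PFS or DoR censoring. Scans are 8-weekly to Week 49 and then 16-weekly, each with a window of ±10 days (SAP Table 1, footnote 13).

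**The concern.** The two documents classify some of the same patient histories differently, and the section meant to announce changes is silent. SAP 4.1.4 does list the change to clinical benefit rate, also a secondary endpoint, so a reader would expect PFS and DoR changes there too.

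The SAP's rules also treat gaps unevenly. As listed, PD found after two missed scans is an event, while a death more than 122 days after the last scan is censored. And because the limit is fixed while the scan interval doubles at Week 49, the same scan history gives an event early in follow-up and a censored time later. DoR is the more exposed endpoint, since responders stay on study longest.

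**Working it through.** **1. The rules side by side (PFS).** Months are study day / 30.4375, as in SAP 8.2.4.

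| History | Protocol 9.4.4 | SAP 11.1.6.2.3 |
|---|---|---|
| PD after two or more missed scans | Censored before the gap | Event, as listed |
| Death over 122 days after last scan, no PD, no new therapy | Event | Censored at last scan |
| Assessments inadequate for RECIST | Not addressed | Censored Day 1 |
| Never scanned, dies by Study Day 122 | Event by the definition; censored by the Day-1 sentence | Event |
| Scan Day 113, new therapy Day 130, death Day 220 (107 days after the scan) | Censored at 113/30.4375 = 3.7 months | Unclear: 3.7 months censored, or event at 220/30.4375 = 7.2 |

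The last row is unclear because the death exception follows the new-therapy clause in the same sentence and can be read as overriding it.

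**2. The SAP's own figure.** Two 8-week intervals plus the window: 2 × 56 + 10 = 122 days, which reproduces. As a study-day label it is one day short: Cycle 5 Day 1 is 4 × 28 + 1 = Day 113, and 113 + 10 = Day 123.

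**3. Against the schedule.** Nominal scans fall on Days 57, 113, 169, 225 (Week 33), 281 (Week 41), 337 (Week 49), 449 (Week 65) and 561 (Week 81).

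| Last scan | Days until the second following window closes | 122-day limit ends |
|---|---|---|
| Week 33 | 337 + 10 − 225 = 122 | Day 347 |
| Week 41 | 449 + 10 − 281 = 178 | Day 403 |
| Week 49 | 561 + 10 − 337 = 234 | Day 459 |

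From Week 49 on, 122 days is one 16-week interval plus the window (112 + 10).

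**4. Consequences for deaths without PD.**

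- One missed scan after Week 33 (window closes Day 291): deaths on Days 292–347 are events.
- One missed scan after Week 41 (window closes Day 347): deaths on Days 348–403 are events, but those on Days 404–459 are censored.
- One missed scan after Week 49 (window closes Day 459): deaths on Days 460–571 are censored.
- No missed scan: the Week 49 scan is done 10 days early, on Day 327, and the Week 65 window stays open to Day 459. A death on Day 455 is 128 days after the scan. The SAP censors at 327/30.4375 = 10.7 months; protocol 9.4.4 and SAP 8.2.4 give an event at 455/30.4375 = 14.9 months. This needs an early scan. If scan dates are assumed uniform within ±10 days, it covers 0.4% of a 16-week interval.

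**5. Size.** The documents give no rates of missed scans, early unscanned deaths or new therapy, so no net effect follows from them. Three partial statements are possible:

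- *Schedule mismatch, PFS.* It starts nominally with the Week 41 scan (Day 281). The last planned PFS rate is at 9 × 30.4375 = Day 274.
- *Schedule mismatch, DoR.* In nine assumed scenarios (true median 6, 12 or 18 months; 5, 10 or 15% stop scanning at a random scan; 3 months from PD to death) the SAP median differed from the protocol median by −0.07 to +0.26 months.
- *Early deaths, if the protocol's Day-1 sentence governs.* With a share q dying unscanned, those patients leave the protocol's risk set at Day 1, so S_SAP(t) = (1 − q) × S_protocol(t) after those deaths. At n = 125 and an assumed PFS of 80%, one such death lowers the rate by 1/125 × 80% = 0.64 points. Under assumed exponential times (median to PD 4–8 months, PD to death 3–6 months), q is 1.5–5.3% and the 3-month rate falls by 1.3–4.0 points. None of these inputs comes from the documents.

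**The case against.** Protocol section 9 lets the SAP modify the plan, and 9.2 leaves specific censoring rules to it. The SAP therefore governs, and it is to be read together with the protocol (SAP 4.0), so the missing gap rule might be supplied from there. A final SAP version is due before database lock. These are descriptive secondary endpoints in non-randomised cohorts. Permission is conceded; what remains is that SAP 4.1 does not disclose the changes, and that a programmer working from the SAP's list would count PD after a gap as an event.

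The early-death exception can be defended. Protocol 9.4.4 defines death without PD as an event and then censors never-scanned patients without mentioning death. The SAP settles that tension in favour of the definition.

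The SAP states a two-assessment intent only for never-scanned patients; applying it after the last scan is an inference. From Week 49 the limit could have been meant as one interval plus the window. That stands, but it does not explain why one missed scan is tolerated after Week 33 and not after Week 49, or why a death with no scan missed can be censored.

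Event definitions are commonly qualified by censoring rules, so SAP 8.2.2 and 8.2.4 are not wrong in themselves; they need a cross-reference. Scheduled scans stop when new therapy starts, so new-therapy censoring in DoR will rarely move a living patient's date. It bears mainly on deaths.

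**Conclusion.** The concern holds as an undisclosed and partly inconsistent set of censoring rules. The omitted gap rule, the limit on late deaths and the Day-1 censoring for inadequate assessments are textual departures from protocol 9.4.4. The 122-day limit and new-therapy censoring in DoR are departures from 9.4.3. The new-therapy sentence for PFS is ambiguous. None appears in SAP 4.1.

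Three stronger readings are not supported:

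- A reader might infer a breach of the protocol. Sections 9 and 9.2 permit the changes.
- A reader might call the early-death exception a clear departure. It conflicts with one protocol sentence and agrees with the protocol's own PFS definition.
- A reader might infer a material bias in the results. The effects run both ways: dropping the gap rule and counting early deaths add events, while the 122-day limit removes them. The net effect cannot be computed.

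The schedule mismatch touches mainly DoR and the late PFS curve, and its effect is probably small. ORR is unaffected. The early-death figures above hold only under their stated assumptions.

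**What to change.** - (a) Restore the protocol's missed-assessment rule in SAP 11.1.6.2.3, so that PD and death after a two-scan gap can be handled alike.
- (b) For PFS and DoR, make the death limit follow the schedule: 122 days if the last scan is at Week 33 or earlier, 178 at Week 41, 234 at Week 49 or later. Alternatively, remove the limit for patients with a post-dose scan. The first option treats PD and death after a gap alike; the second returns to the protocol, which censors such PD but counts the death. Refer to the chosen rule from SAP 8.2.2 and 8.2.4.
- (c) Keep the early-death exception, which matches the PFS definition, and list it in SAP 4.1 as a change from protocol 9.4.4. Correct the Day 122/123 label at the same time.
- (d) State that deaths after new anti-cancer therapy are censored for PFS, as protocol 9.4.4 says.
- (e) List the remaining departures in SAP 4.1, including Day-1 censoring for inadequate assessments and new-therapy censoring for DoR.

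The cost is SAP wording and minor programming. No new data are needed, and the final SAP version before database lock is the natural place.

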11.1.6.2.4 Overall Survival (OS)

OS will be summarized similarly to PFS. Additionally, the 1-year OS rate (proportion and 95% CI) will be analyzed using KM methodology (Greenwood's formula, Kalbfleisch and Prentice, 1980).

Censoring Rules for OS

For patients who are continuing the study at the time of an analysis, lost to follow-up, or who withdrew consent, the OS endpoint will be censored on the last date that patients were known to be alive. The date last known to be alive is derived from the CRF and may include but not limited to the latest visit date for patients ongoing in the study or the latest Date of Contact on the Long-Term Follow-up/Survival Status page, whichever occurs latest. For patients with no follow-up after the first dose of study drug, OS will be censored at the date of first dose.

11.1.6.2.5 Extent of Follow-Up

The median extent of follow-up with 95% CI will be calculated and presented in a dedicated table using a reverse KM approach (reversing the OS censoring).

11.1.7 Safety Analyses

All safety analyses will be summarized by actual treatment arm.

DLTs will be presented using the DLT Evaluable Population, all other safety parameters will be presented using the Safety Population.

11.1.7.1 Extent of Study Drug Exposure

Descriptive statistics will be provided separately for each study drug, for the duration of exposure (weeks) and the total number of cycles started. The number of doses administered, cumulative dose administered (mg), relative dose intensity and overall compliance will be presented for Sitravatinib only.

For Glesatinib and Sitravatinib, the number and percentage of patients will also be presented for patients with at least one dose reduced from the previous dose, and at least one dose interrupted, along with all associated reasons.

For Nivolumab the number and percentage of patients will also be presented for patients with at least one dose interrupted or delayed from the previous, and at least one infusion interrupted along with all associated reasons.

Information regarding patients' dosing regimens will be listed separately for each investigational study drug.

11.1.7.2 Treatment Emergent Adverse Events (TEAEs)

All AEs will be coded according to the Medical Dictionary for Regulatory Activities (MedDRA) v19.0 dictionary by SOC, PT, and severity grade using NCI CTCAE v4.03.

An overall summary of TEAEs will be presented, with supporting tables summarizing TEAEs by SOC and PT, as well as PT only. Counts will be presented by patient rather than event and those experiencing multiple instances of the same event will be counted only once within each SOC or PT.

The following summaries will be presented by SOC and PT for the Sitravatinib plus Nivolumab treatment arm, using the Safety Population, unless otherwise specified.

- Any TEAEs
- Any DLTs (DLT Evaluable Population)
- Any Treatment-Related TEAEs
- Any Nivolumab-Related TEAEs
- Any Sitravatinib-Related TEAEs
- Any TEAE leading to dose reduction or interruption of either study drug
- Any Treatment-Related TEAE leading to dose reduction or interruption of either study drug
- Any TEAE leading to drug discontinuation of either study drug
- Any TEAE leading to Nivolumab discontinuation
- Any TEAE leading to Sitravatinib discontinuation
- Any Treatment-Related TEAE leading to drug discontinuation of either study drug
- Any Nivolumab-Related TEAE leading to Nivolumab discontinuation
- Any Sitravatinib-Related TEAE leading to Sitravatinib discontinuation
- Any TEAE leading to study discontinuation
- Any TEAEs by Maximum CTCAE Grade
- Any Treatment-Related TEAEs by Maximum CTCAE Grade
- Any Nivolumab-Related TEAEs by Maximum CTCAE Grade
- Any Sitravatinib-Related TEAEs by Maximum CTCAE Grade
- Any irAEs

- Any AESIs (if at least one AESI is identified)

For the Glesatinib and Nivolumab treatment arm, a single summary table by SOC and PT will be presented.

- Any Glesatinib-Related TEAEs

In addition to the SOC and PT summaries, the following summaries will also be presented by PT only for the Sitravatinib plus Nivolumab treatment arm

- Any TEAEs
- Any TEAEs by Maximum CTCAE Grade (Any Grade, Grade 3, Grade 4, Grade 5)
- Any Treatment-Related TEAEs by Maximum CTCAE Grade (Any Grade, Grade 3, Grade 4, Grade 5)
- Any Nivolumab-Related TEAEs by Maximum CTCAE Grade (Any Grade, Grade 3, Grade 4, Grade 5)
- Any Sitravatinib-Related TEAEs by Maximum CTCAE Grade (Any Grade, Grade 3, Grade 4, Grade 5)

All TEAEs will be listed, separate listings for irAEs and TEAEs leading to study drug discontinuation (TEAEs and related TEAEs) will also be presented.

11.1.7.3 Serious Adverse Events (SAEs) and Deaths

The following summaries of treatment emergent SAEs, including TEAEs that lead to death, will be presented by SOC and PT for the Sitravatinib plus Nivolumab treatment arm, using the Safety Population:

- Any Treatment-Emergent SAEs
- Any Treatment-Related Treatment-Emergent SAEs
- Any Nivolumab-Related Treatment-Emergent SAEs
- Any Sitravatinib-Related Treatment-Emergent SAEs
- Any TEAE with an outcome of death

In addition to the SOC and PT summaries, the following summaries will also be presented by PT only for the Sitravatinib plus Nivolumab treatment arm

- Any Treatment-Emergent SAEs
- Any Treatment-Related Treatment-Emergent SAEs

All treatment emergent SAEs and TEAEs with an outcome of death will be listed.

11.1.7.4 Laboratory Data

Laboratory data will be presented for hematology, chemistry, urinalysis and thyroid function tests (see Table 6 for a list of specific parameters under each category), by scheduled visit using the Safety Population for patients with at least 1 measurement for each parameter, regardless of whether or not a baseline assessment is present. Unscheduled visits will be included in any presentation of minimum, maximum or worst case summaries across all cycles.

All laboratory data will be summarized in International System (SI) units, with selected chemistry parameters repeated using British imperial units commonly used in the United States. The conversion factors from conventional units to SI units are documented in the Lab Loader Specification (v1.0 October 13th 2020) for this study.

Descriptive statistics will be provided for each parameter result and associated changes from baseline by cycle. Multiple measurements taken during a given visit for a patient will be represented by the most severe value for each parameter. Criteria for selecting the most severe value in these cases are described in the category specific sections below.

Shift tables for selected parameters will present shifts in CTCAE grades from baseline to each post-baseline scheduled visit, to the maximum post-baseline grade (including unscheduled visits), and to the last assessment.

All clinical laboratory results will be listed, with any laboratory values meeting NCI CTCAE Grade 3 or 4 criteria being listed separately.

CTCAE Coding of Laboratory Data

Grades are applied based only on the numeric SI value of the parameter assessed; clinical signs and symptoms are not considered. For example, Grade 4 hyperglycemia will be assigned based solely on the value of the glucose measurement, and acidosis will not be considered. Where categories are only distinguished by clinical signs or symptoms, the lowest of the possible grades will be assigned.

NCI CTCAE grades will be applied for the following lab parameters:

- Hematology: hemoglobin, WBC, lymphocyte, neutrophils, and platelets.
- Chemistry: ALT, albumin, alkaline phosphatase, AST, total bilirubin, calcium, creatinine, magnesium, potassium, sodium, uric acid.

Laboratory measurements that are within their institutional limits of normal and are not graded as 1-4, per the CTCAE, will be summarized as "Grade 0," which is defined as normal.

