7.2.3 Laboratory Safety Assessments

Laboratory safety assessments for which data will be collected in this study will include hematology, coagulation, thyroid tests, urinalysis and chemistry parameters presented in Table 19.

Laboratory tests will be drawn at the time points described in the Schedule of Assessments (Table 1) and analyzed at local laboratories. Additional laboratory tests may be performed per standard of care, at the Investigator's discretion for the purpose of planning treatment administration, dose modification, following adverse events, or as clinically indicated.

Table 19: Laboratory Safety Parameters

Hematology Panel	Blood Chemistry Panel	
Hemoglobin	Aspartate aminotransferase (AST)	
Platelet count	Alanine aminotransferase (ALT)	
White blood cell count (WBC)	Alkaline phosphatase	
Neutrophil count	Total bilirubin (if Total bilirubin is ≥2×ULN and no evidence of Gilbert's syndrome, then fractionate into direct and indirect bilirubin)	
Lymphocyte count	Lipase	
	Amylase	
Coagulation	Sodium	
International normalized ratio (INR)	Potassium	
Partial thromboplastin time (PTT)	Chloride	
	Bicarbonate [CO ²]	
Urinalysis (dip stick)	Blood urea nitrogen (BUN)	
Blood	Creatinine	
Protein	Glucose (non-fasted)	
	Albumin	
Thyroid Function Test	Total Calcium	
Thyroid-stimulating hormone (TSH)	Magnesium	
Free-T4	Uric acid	

Pregnancy Testing: For patients of childbearing potential, a serum or urine pregnancy test will be performed by the local laboratory at screening. Pregnancy tests will also be done whenever pregnancy is suspected during the study. Additional pregnancy testing may be necessary if required by local practices or regulations.

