Pregnancy Test ⁵	X								
Hematology ^{6,7}	X	X	X	X	X	X	X	X	

As clinically indicated

Table 1: Schedule of Assessments (Continued)

Assessments	Screen/ Baseline		Cycle 1		Cycle 2 and 3		≥ Cycle 4		End of Treatment ¹⁵	
	Within 28 days	Day 1 (± 2 days)	Day 15 (± 2 days)	Day 1 (± 2 days)	Day 15 (± 2 days)	Day 1 (± 2 days)	Day 15 (± 2 days)	Day 15 (± 2 days)	End of Treatment/ Withdrawal	Post Treatment Follow Up
Coagulation ^{6,7}	X								As clinically indicated	
Urinalysis ^{6,7}	X								As clinically indicated	
Serum Chemistry ^{6,7}	X	X	X	X	X	X	X	X		X
Thyroid Function Test ^{6,7}	X	X		X			X			X
Blood for Pharmacokinetics ⁸										
Biopsy of Tumor for Biomarker Studies (Optional) ⁹										
Blood Samples – Flow Cytometry ¹⁰										
Blood Samples – Protein and Cytokine Biomarkers ¹⁰										
ctDNA blood sample ¹¹	X									
Single 12-Lead ECG ¹²	X									
Triplete 12-Lead ECG ¹²										

See Table 2, Table 3, and Table 4 and Table 4 and Table 23, Table 24, Table 25 from the protocol sub-study appendix 5 and appendix 6 for PK sub-studies

Table 1: Schedule of Assessments (Continued)

Assessments	Screen/ Baseline	Cycle 1		Cycle 2 and 3		≥Cycle 4		End of Treatment ¹⁵	
	Within 28 days	Day 1 (± 2 days)	Day 15 (± 2 days)	Day 1 (± 2 days)	Day 15 (± 2 days)	Day 1 (± 2 days)	Day 15 (± 2 days)	End of Treatment/ Withdrawal	Post Treatment Follow Up
Echocardiogram (Mocetinostat and Sitravatinib Treatment Arms Only)	X		X Mocetinostat arm only	X Cycle 3 only		X Mocetinostat arm only		X	
Disease Evaluation ¹³	X				Every 8 weeks (± 10 days) for ~1 year and then every 16 weeks				
Investigational Agent Dispensing and/or Reconciliation		X		X		X			
Nivolumab Administration		X	X if Q2W	X	X if Q2W	X	X if Q2W		
Adverse Events ¹⁴ and Concomitant Medications	SAEs only								
Long Term Follow-up ¹⁶					Throughout				X

- 1 Study Participation Informed Consent: May be performed more than 28 days prior to the first dose of study treatment and must be completed prior to initiation of any study specific assessments.

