**Table 6:**

Hematology Panel	Chemistry Panel

 • Hemoglobin ^{High or Low} • Platelet Count • White Blood Cell (WBC) Count • Neutrophil Count • Lymphocyte Count ^{High or Low} • International Normalized Ratio (INR) • Partial Thromboplastin Time (PTT) 	
 • Alkaline Phosphatase • ALT • AST • Total Bilirubin ^{IU} • Direct Bilirubin ^{IU} • Indirect Bilirubin ^{IU} • Lipase • Amylase • Creatinine ^{IU} • Blood Urea Nitrogen (BUN) ^{IU} • Chloride ^{Low} • Bicarbonate [CO₂] ^{Low} • Sodium ^{High or Low} • Potassium ^{High or Low} • Glucose (Non-Fasted) ^{High or Low} • Albumin ^{Low} • Calcium ^{High or Low / IU} • Magnesium • Uric Acid
Urinalysis (Dip Stick)	

 • Blood • Protein 	
Thyroid Function Test	

 • Thyroid Stimulating Hormone (TSH) • Free-T4 	

IU: Indicates Chemistry parameter that will be summarized twice, once in SI units and once in Imperial units.

Low: Indicates Chemistry parameter where most severe values are low.

High or Low: Indicates parameter where most severe values can be in either direction.

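### INR, PTT and the bilirubin fractions go into by-cycle and change-from-baseline tables although none is measured routinely on treatment, so those tables describe selected patients

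*SAP*

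**What the plan says.** SAP 11.1.7.4 sets one rule for the laboratory panels in its Table 6: "Descriptive statistics will be provided for each parameter result and associated changes from baseline by cycle". Results are shown "by scheduled visit using the Safety Population for patients with at least 1 measurement for each parameter". A missing baseline does not exclude a patient. For tests outside the schedule it adds: "Unscheduled visits will be included in any presentation of minimum, maximum or worst case summaries across all cycles". SAP 11.0 rules out imputation and carrying values forward unless otherwise noted.

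Table 6 places INR and PTT in the hematology panel without a direction mark. Direct and indirect bilirubin are in the chemistry panel, both marked to be summarized in two unit systems. SAP 11.1.7.4.1 treats low values as the severe direction for every hematology parameter not marked otherwise. SAP 11.1.7.4.4 and 11.1.7.4.5 make urinalysis and thyroid results listing-only. No section does this for the four parameters at issue.

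The measurement schedule is different. In the schedule of assessments (Table 1 of both documents) coagulation is due at screening and then "As clinically indicated". Protocol 7.2.3, Table 19, has no routine measurement of the fractions. Under total bilirubin it says that, at 2 × ULN or more with no evidence of Gilbert's syndrome, the site should "then fractionate into direct and indirect bilirubin".

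**The concern.** A by-cycle table with change from baseline is meant to show how a parameter moves over time in the treated population. That reading needs roughly the same patients at each time point. Here the patients with a value at a cycle are those for whom someone saw a reason to test.

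The study is not randomized (SAP 6.3) and has no nivolumab-alone arm, so no comparator would share the same selection and reveal it. The tables also touch questions the protocol itself raises: it calls the hemorrhagic risk of sitravatinib unknown (5.1.2.4.4) and has dedicated rules for transaminase rises and Hy's Law cases (5.1.4.2.3 and 5.1.4.2.4). A drift produced by who was tested could be taken for a drug effect.

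**Working it through.** The plan states no figure to reproduce. The check sets the schedule against the planned display, then asks what each table would contain.

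**Schedule against display**

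| Parameter | Screening | On treatment | SAP display |
|---|---|---|---|
| INR, PTT | all patients | when indicated | by cycle, with change |
| Urinalysis | all patients | when indicated | listing only |
| TSH, free T4 | all patients | Day 1 of every cycle | listing only |
| Direct, indirect bilirubin | only if total ≥ 2 × ULN, no Gilbert's | same condition | by cycle, with change, in two unit systems |

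Urinalysis has the same schedule as coagulation but is only listed. Thyroid tests are measured every cycle and are also only listed. The SAP gives no reason for treating INR and PTT differently.

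**INR and PTT**

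Suppose nothing changes over time, and measure values in SD units. Let ρ be the correlation between a patient's baseline and later value, k the correlation between the reason for testing and the current value, and λ the mean of the top tested share of a standard normal. For 5%, 10% and 20% tested, λ is about 2.06, 1.76 and 1.40. Among those tested:

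- mean result at the cycle = k × λ, against an all-patient baseline mean of 0;
- mean change from baseline = k × λ × (1 − ρ).

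All inputs are assumptions; the documents give none. With 5–20% tested and ρ from 0.5 to 0.7:

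- k = 0: result 0, change 0.
- k = 0.3: result 0.3 × 1.40 = 0.42 to 0.3 × 2.06 = 0.62 SD; change 0.42 × 0.3 = 0.13 to 0.62 × 0.5 = 0.31 SD.
- k = 0.6: result 0.84 to 1.24 SD; change 0.84 × 0.3 = 0.25 to 1.24 × 0.5 = 0.62 SD.
- k = 1.0: change 1.40 × 0.3 = 0.42 to 2.06 × 0.5 = 1.03 SD.

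Of the 125 patients in the combined CIT-experienced sitravatinib cohort, these shares are about 6 to 25 patients per cycle (0.05 × 125 = 6.25; 0.20 × 125 = 25).

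**Bilirubin fractions**

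Protocol 4.1, criterion 6, caps bilirubin at 1.5 × ULN, or at 3.0 × ULN with Gilbert's syndrome or liver metastases. Set this against the trigger of 2 × ULN without Gilbert's:

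- capped at 1.5 × ULN: 1.5 < 2, so screening cannot trigger a fraction;
- Gilbert's syndrome: outside the trigger;
- liver metastases without Gilbert's: a fraction is triggered only at 2 to 3 × ULN.

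A triggered baseline fraction is thus confined almost entirely to the last group. It is not strictly impossible elsewhere: under SAP 8.1.1 baseline is the last pre-dose value, so a Cycle 1 Day 1 result could exceed the screening cap, and a site may fractionate for its own reasons.

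As an illustration, total bilirubin was simulated as lognormal with median 0.5 × ULN, log-SD 0.5–0.7, correlation 0.5–0.7 and no drift, and with everyone allowed the generous 3 × ULN cap. All of these are assumptions.

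- About 0.3% to 2.2% of patients would be fractionated at one later visit: 0.0027 × 125 = 0.3 to 0.0224 × 125 = 2.8 of 125 patients.
- Only about 7% to 24% of those would also have a baseline fraction.
- Mean total bilirubin behind the fractions is about 2.3–2.4 × ULN at baseline and 2.3–2.7 × ULN later.
- Where both exist, total bilirubin rises by about 0.1 to 0.45 × ULN, mainly because the cap limits baseline but not later values.

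The fault here is a missing baseline and a level that is high throughout.

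**The case against.** A reader might infer that all four parameters are measured only when something is wrong, so that their trends must worsen. The documents do not support that.

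- For the fractions, the Table 19 trigger has no visit restriction. Selection acts at screening too, so there is no unselected baseline and no steep built-in trend.
- For INR and PTT, a clinical indication need not be an abnormality. Protocol 7.2.3 also allows tests under standard of care and for planning treatment. Protocol 5.4.1 bars therapeutic warfarin only with mocetinostat, so a sitravatinib patient could have routine INR monitoring. If testing is unrelated to the value, the bias is zero.
- Change from baseline is a within-patient difference. Subtracting an all-patient baseline mean from the mean of those tested overstates it, as the factor (1 − ρ) shows.

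Other points also limit the concern. An indicated test at an unscheduled visit stays out of the by-cycle tables. With several INR or PTT values in one visit, the hematology default picks in the low direction, which works against apparent worsening. All laboratory results are listed. None of the four parameters is CTCAE-graded or in a shift table, and the Hy's Law figures use total bilirubin. No test, sample size or stopping rule depends on these tables.

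All of this stands, and it rules out any claim of certain or quantified bias. It does not rescue the tables. Indicated tests drawn at a Day 1 or Day 15 visit still enter them, and a within-patient difference remains selected whenever the reason for testing is related to the current value. The rule on unscheduled visits applies to whatever minimum, maximum or worst-case displays are produced; it does not commit the SAP to one for INR or PTT. The low-direction default is a further fault, since the protocol's bleeding concern points to high values.

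**Conclusion.** The point holds in a limited form and is minor. Followed as written, SAP 11.1.7.4 and Table 6 produce by-cycle tables for four parameters that do not describe the Safety Population over time.

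For INR and PTT, the results and changes are likely, though not certain, to look worse without any drug effect. The size cannot be derived from the documents. The illustration gives 0 to about 1 SD for the change, and 0.13 to 0.62 SD at k between 0.3 and 0.6, resting wholly on assumed correlations and tested shares.

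For the bilirubin fractions, the conclusion that baseline is nearly absent rests on the documents' own trigger and eligibility caps. The percentages rest on the assumed distribution.

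The effect is confined to descriptive safety tables.

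**What to change.** In SAP 11.1.7.4 and Table 6:

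- Take INR, PTT, direct bilirubin and indirect bilirubin out of the by-cycle and change-from-baseline tables.
- For INR and PTT, show the screening value, the number tested on treatment and the worst on-treatment value among those tested, with unscheduled visits included.
- Mark INR and PTT as High in Table 6 and add that mark to its key, so that the low-is-severe default in 11.1.7.4.1 no longer applies to them.
- List the fractions beside total bilirubin for every patient fractionated. Confining them to the Hy's Law listing would lose patients with an isolated bilirubin rise, because the at-risk criteria in 11.1.7.4.3 also require ALT or AST at 3 × ULN.

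The cost is SAP wording: a few by-cycle tables are lost and one small table is added. SAP 4.0 provides for a final version before database lock, which is the place for the change.
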